4.6 Subject withdrawal criteria

A subject may withdraw from the study at any time at his/her own request without prejudice to future medical care. Subjects may also be withdrawn at any time at the discretion of the investigator for safety, compliance, or administrative reasons.

If a subject does not attend a required study visit, the following actions will be taken:

- The site will attempt to contact the subject at least twice and reschedule the missed visit as soon as possible. Every effort to regain contact with the subject will be made (e.g., telephone contact on different dates/times, registered mail). All contact attempts will be documented.
- If attempts to contact the subject are not successful, then the subject will be considered lost to follow-up and withdrawn from the study. The reason for early withdrawal will be documented in the eCRFs.

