All scheduled visits and applicable study assessments must occur as noted in [Section 5.1](#) and the Schedule of Events table ([Appendix 11.1](#)).

5.1.2 *Unscheduled visits*

To ensure subject safety during the study, any subject who requires additional follow-up during the study for any reason (that does not fall on a scheduled study visit) should have that visit recorded as an unscheduled visit; additionally, all applicable eCRFs for that unscheduled visit should be completed (e.g., AEs, concomitant medications/ procedures).

5.2 *Stopping rules*

5.2.1 *Criteria for treatment discontinuation*

If study treatment is discontinued at any time during the treatment administration, the investigator will record the reason for treatment discontinuation in the study records. The investigator may request that a subject discontinuing treatment continue to participate in the study and complete all remaining visits and assessments. If a subject declines to continue study participation, the investigator will make every effort to perform the appropriate assessments specified in the Schedule of Events ([Section 5.1](#) and [Appendix 11.1](#)).

5.2.2 *Premature suspension or termination of the study*

Should the investigator, sponsor, the FDA, or local regulatory authorities become aware of conditions arising during the conduct of this study that may warrant the cessation of the study, such action may be taken. Prior to such action, consultation between the sponsor, the investigator, and, as appropriate, the FDA and/or local regulatory authorities will occur.

In the case of a reported vascular embolic event leading to skin necrosis, vision loss, or stroke, the study will be suspended, and a root-cause investigation will be conducted to determine the cause of the embolic event and whether the outcome was anticipated or unanticipated. If the latter situation is observed, the entire study will be immediately suspended and no subjects will be enrolled until the event can be properly characterized and an appropriate treatment strategy to avoid this unanticipated event can be devised.

Reasons for the premature suspension or termination of the study include, but are not limited to, the following:

- Determination of a potential safety risk to subjects;
- Inadequate subject enrollment;
- Decision by the IEC/IRB to suspend or terminate approval/favorable opinion for the study;
- Sponsor decision; and/or

- Other.

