In the event of premature study suspension or termination for safety reasons, the sponsor will inform all investigators and relevant regulatory authorities promptly of the study suspension/termination and reason for the action. The investigator will conduct site-closure activities in accordance with all applicable sponsor and local/international guidelines and regulations.

5.2.3 *Study site discontinuation*

Study participation by individual sites may be discontinued by the sponsor for any of the reasons listed in [Section 5.2.2](#). Additional reasons for the premature discontinuation of study sites include, but are not limited to, the following:

- Investigator request;
- Serious or persistent noncompliance with the protocol, local regulations, and/or GCP;
- Failure to accrue subjects at an acceptable rate;
- Ethical issues; and/or
- Other.

In the event of study site discontinuation, the sponsor will provide to the study site written notification documenting the reason for discontinuation. The investigator will conduct site-closure activities in accordance with all applicable sponsor and local/international guidelines and regulations.

5.2.4 *Discontinuation criteria for a subject*

Each subject will be followed to the end of the study, or if/when the sponsor decides to terminate the study, whichever comes first. The only reasons a subject will not be followed for all scheduled visits are withdrawal of consent or lost to follow-up (e.g., moving away from study site; unresponsive to attempts to contact the subject).

If a subject withdraws consent to continue in the study, the investigator should make every attempt to complete the final study visit. If a non-serious AE is unresolved at the time of the subject's final study visit, an effort will be made to follow-up until the AE is resolved or stabilized, the subject is lost to follow-up, or there is some other resolution of the event. The investigator should make every attempt to follow all SAEs/UADEs to resolution. Information on pregnancy and the outcome for any female who becomes pregnant during the study will be collected. Additional information on subject withdrawal criteria is provided in [Section 4.6](#).

5.2.5 *Provision of care for subjects after study discontinuation*

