6.3 Study treatment

All protocol-specific criteria for the administration of study treatment must be met and documented prior to administration of any study treatment. All device administration (injection) will be performed on site by the principal investigator (PI); only the PI can inject. The PI is also described as the treating investigator in this document. Subjects will not be dispensed any investigational material. Any noncompliant subject or site may be discontinued from the study ([Section 5.2](#)).

6.3.1 *Planned treatment procedure and administration*

Subjects will receive treatment with Belotero Balance with integral lidocaine (Test product) and Belotero Balance without lidocaine (Control product).

At baseline, approximately 52 subjects will be randomized in this split-face study. Prior to injection, one NLF will be randomized to receive Belotero Balance with integral lidocaine (Test), and the contralateral NLF will receive Belotero Balance without lidocaine (Control).

A single randomization scheme will determine which NLF (subject's right or left) will be assigned to Test product or Control product and which NLF (subject's right or left) will be injected first. Randomization will be provided by an electronic randomization system, which site personnel must access following confirmation that the subject meets all eligibility criteria.

Care must be taken to follow the subject's randomization assignment – ensuring the Test product and Control product syringes are injected according to their assigned order (Test first or Control first) and into the NLF that is randomly assigned to be injected first (subject's right NLF first or subject's left NLF first). Accurate documentation of (1) which product (Test or Control) is injected into which NLF (subject's right or left) and (2) in the order assigned by the randomization system

(subject's right NLF first or subject's left NLF first) is of critical importance in this study.

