7.2.4 Procedures for reporting specific events

7.2.4.1 Adverse event (AE) and adverse device effect (ADE)

Subjects will be carefully monitored during the clinical investigation for possible AEs and ADEs.

The period of observation for AEs and ADEs extends from signing of the informed consent form (ICF) until the subject’s last visit. Any medical occurrence between the time the ICF is signed and the first treatment with the investigational medical device is classified as an AE or ADE and must be documented in the subject’s file and in the eCRF. New AEs or ADEs reported to the investigator during the observational period (i.e., after the start of treatment with the investigational medical device) must also be documented, treated, and followed.

Any AE, ADE, and/or device deficiency observed during study conduct will be fully investigated, documented, and followed until the event is either resolved, until the

condition stabilizes, until the event is otherwise explained, or the subject is lost to follow-up.

The investigator will assess and record any AE or ADE in detail in the subject's file (medical record) and in the eCRF AE report form. At a minimum, the following information will be recorded:

- AE diagnosis or main symptom
- Location of AE: systemic or restricted to injection area. In case of local reaction, the corresponding area should be reported.
- Start and stop dates
- Severity/Intensity
- Causal relationship
- Serious (yes or no)
- Outcome
- Action taken with investigational medical device
- AE resulting in subject discontinuation (yes or no)

7.2.4.2 *Serious adverse event (SAE) and serious adverse device effect (SADE)*

The investigator must report all SAEs and SADEs that occur during the observational period on the SAE form, within 24 hours, whether considered related or not related to the investigational device.

The investigator must report SAEs and SADEs to Merz or designee as defined in [Section 7.2](#) and the site's IEC/IRB per their reporting guidelines.

Although all information required for completing an SAE report form may not be available within the specified time period, an initial report should be submitted and the following minimal information should be provided:

- An identifiable subject number;
- Adverse event;
- Investigational device name;
- Causality or relationship of investigational device; and/or
- Investigator/investigational site name.

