7.2 Safety Variables

All safety analyses will be performed on the SES.

AEs will be coded according to the Medical Dictionary for Regulatory Activities (MedDRA, version 20.0). Only treatment emergent adverse events (TEAEs) will be analyzed, which are defined as AEs with onset or worsening after the administration of the study drug. Incidences will be calculated for TEAEs on the system organ class level and on the preferred term level (total, by intensity, and by relationship – related or not related). Listings and tables displaying incidences for TEAEs leading to discontinuation and serious TEAEs will also be provided.

TEAEs associated with NLFs will be summarized by treatment. All TEAEs will be summarized without by-treatment breakdown.

In summaries by system organ class and preferred term each subject will be counted once per preferred term and treatment if applicable. Similarly in summaries by system organ class each subject will be counted once per system organ class and treatment if applicable. In summaries that are additionally broken down by intensity or relationship, subjects with multiple events will be summarized by the worst severity or worst relationship, as applicable.

Number and percentage of subjects with CTR, as well as the number of continuous CTR episodes, will be summarized by treatment and maximum severity as well as by treatment and maximum duration. Duration will be classified as 1-3 days, 4-7 days, 8-14 days 15-30 days and > 30 days.

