7.4 Special Statistical/Analytical Issues

7.4.1 Discontinuations and Missing Data

Imputation of effectiveness data

Observed Cases (OC)

- For the OC method, there will be no missing value imputations conducted. All effectiveness data will be analyzed as observed data.

Last Observation Carried Forward (LOCF)

- For the LOCF, in the analysis of the secondary effectiveness variable the subjects who have a missing score on the Merz NLF scale at Week 6 will have their latest available assessment (from the early discontinuation or unscheduled visit if available; failing

that, from the baseline visit) carried forward and imputed into the missing Week 6 assessment.

Imputation of safety data

For partial or completely missing start date of adverse events, the following imputation rules related to any treatment period will be used if applicable:

- If only the day is missing for any date used in a calculation, the 1st will be used to replace the missing day. If the new estimated date falls before the date of first dose, while the known month and year match the month and year of the first dose, the date of first dose will be used as the new estimated date.
- If the day and the month are missing, no estimation will be performed. However, if the year of onset is the same or greater than the year of the first dose date, the AEs will be considered treatment emergent and included in the summary tables.
- AEs with completely missing onset dates will be considered treatment emergent; no estimation of the dates will be performed.

Duration of CTRs would be computed using the following logic:

- Each subject is expected to have diary entries from Day 1 (day of the initial injection) up to and including Day 42 or the day of their completion/discontinuation, whichever comes first. If any subject does not have a diary entry for any of the required days, then for the purposes of CTR analysis it will be assumed that on the missing days they had all those CTRs (if any) that they had on the day before or on the day after the missing day, with the same severity.
- For any CTR with an uninterrupted single episode event, the duration will be computed as the days from the beginning of event to last date of event.
- For any CTR with multiple episodes, the CTR will be regarded as a continuous event if the date between paired episodes is not more than 1 day apart.

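### Protocol 4.6 and 6.3 contradict 5.2.4 on whether a withdrawn subject is still followed, and the SAP records a treatment-site response still present at the last diary entry as if it had resolved

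*Protocol*

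**What the plan says.** Three protocol sections deal with a subject leaving early.

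- **4.6** gives the investigator discretion: "Subjects may also be withdrawn at any time at the discretion of the investigator for safety, compliance, or administrative reasons".
- **6.3** says: "Any noncompliant subject or site may be discontinued from the study". It refers to 5.2 and does not say who decides.
- **5.2.4** makes a general commitment, "Each subject will be followed to the end of the study, or if/when the sponsor decides to terminate the study, whichever comes first", and then closes the list of exceptions: "The only reasons a subject will not be followed for all scheduled visits are withdrawal of consent or lost to follow-up". It points back to 4.6 for more on withdrawal.

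Section 5.2.1, on treatment stopped in the course of administration, says: "The investigator may request that a subject discontinuing treatment continue to participate in the study and complete all remaining visits and assessments".

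On the analysis side, SAP 7.4.1 expects diary entries from Day 1 "up to and including Day 42 or the day of their completion/discontinuation, whichever comes first". Missing days are filled from neighbouring days only within that window. The duration of a CTR runs from its start to its last recorded date. SAP 7.2 groups durations into 1-3, 4-7, 8-14, 15-30 and more than 30 days. It also promises: "Listings and tables displaying incidences for TEAEs leading to discontinuation and serious TEAEs will also be provided". CTR incidence, severity and duration form a stated safety endpoint (Protocol 2.2.4, SAP 6.2).

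**The concern.** A site that withdraws a subject under 4.6 cannot tell whether to stop data collection or to continue it as 5.2.4 requires. Two sites could act differently and both cite the protocol.

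The choice matters because one ground in 4.6 is safety, and the diary measures how long treatment-site reactions last. If withdrawal ends the diary, a reaction still present that day enters the duration table with the length observed so far, and nothing marks it as unresolved. The affected outputs would be the CTR duration table, AEs that first appear after the subject leaves, and the observed Week 6 Merz rating behind the secondary endpoint.

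**Working it through.** **Step 1: the protocol text.**

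| Section | Who decides | Ground | Consequence |
|---|---|---|---|
| 4.6 | Investigator | Safety, compliance, administrative | Withdrawn from the study |
| 6.3 | Not named | Noncompliance | Discontinued from the study |
| 5.2.4 | Subject, or circumstance | Consent withdrawn, or lost | The only exceptions to full follow-up, apart from sponsor termination |

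None of the grounds in the first two rows appears in the third, which calls itself exhaustive. The cross-reference from 5.2.4 to 4.6 leads to the conflicting rule and does not resolve it. Two clauses try to rescue data after an early exit. The one in 5.2.1 applies when the subject declines to continue, and the one in 5.2.4 applies when the subject withdraws consent. Neither is written for withdrawal by the investigator.

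**Step 2: the plan's own figures.** The plan gives no figure for this point. Its sample sizes serve only as denominators. With a difference of 3.8, SD of differences 7, one-sided alpha 0.025 and 95% power, a paired t-test with the noncentral t distribution gives 47 (power 95.4%; 46 subjects give 94.97%), as stated. 47 × 1.10 = 51.7, which rounds to the stated 52.

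**Step 3: what the SAP rule records.** For a CTR still present when the diary ends:

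recorded duration = last diary day − onset day + 1.

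With onset on Day 1 and withdrawal on Day 10, this is 10 − 1 + 1 = 10 days, class 8-14. If the same CTR persisted and were followed to Day 42, it would be 42 − 1 + 1 = 42 days, class >30. Counting elapsed days instead (9 and 41) gives the same classes. Further cases with onset on Day 1 and assumed true durations:

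| True duration | Diary ends | Recorded | True class | Recorded class |
|---|---|---|---|---|
| 20 days | Day 7 | 7 | 15-30 | 4-7 |
| 20 days | Day 14 | 14 | 15-30 | 8-14 |
| 35 days | Day 7 | 7 | >30 | 4-7 |
| 35 days | Day 14 | 14 | >30 | 8-14 |
| 35 days | Day 21 | 21 | >30 | 15-30 |
| 35 days | Day 42 | 35 | >30 | >30 |

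The shift is one to three classes. Both folds stop on the same day, so the fold with the longer reaction loses more. A difference in duration between products would tend to shrink.

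**Step 4: the reason for the exit does not matter.** The same arithmetic applies after withdrawal of consent or loss to follow-up. It can also apply to a completer: a CTR that starts on Day 14 and is still present on Day 42 is recorded as 42 − 14 + 1 = 29 days, class 15-30.

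**Step 5: size per subject.** 1/52 = 1.9% and 1/47 = 2.1%. Two subjects of 52 are 3.8% and three are 5.8%. This counts only subjects whose CTR truly belonged in a longer class. The 10% allowance in Protocol 8.1 covers loss between randomization and treatment, so it says nothing about withdrawals after injection.

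**Step 6: Week 6 rating.** In the observed-case analysis the subject's pair drops out of McNemar's test. Under the LOCF rule in SAP 7.4.1, a rating from an early-discontinuation or unscheduled visit is used and, failing that, the baseline rating. A carried baseline means zero change, so both folds count as non-responders. That pair is concordant: it lowers both responder rates but does not enter McNemar's statistic.

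**The case against.** The strongest reply is that the reactions that matter most are protected elsewhere. Protocol 7.1.8 has the investigator evaluate a CTR that is unusually severe or not resolving as a possible AE. Section 7.2.4.1 requires AEs to be followed until resolved, stabilized, otherwise explained or lost, with start and stop dates recorded. Section 5.2.4 extends follow-up of unresolved events past the final visit. A reaction bad enough to prompt a safety withdrawal is an obvious candidate for this route. The secondary endpoint is also analysed with and without imputation (SAP 8). All of this stands, and it narrows the effect. It does not correct the CTR duration table, which is built from the diary.

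A second reply is that the truncation comes from the SAP and would remain if 4.6 and 5.2.4 agreed. That is correct (Step 4), and it is why two separate changes are needed.

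Four stronger readings may tempt a reader, and the documents do not support them:

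- *Section 6.3 also lets the investigator remove subjects for safety.* It names neither the investigator nor safety. The safety ground rests on 4.6 alone.
- *Section 5.2.1 makes follow-up optional after any reaction.* It concerns treatment stopped during administration, and it asks for every effort to complete assessments if the subject declines to continue.
- *Under 5.2.4 an AE can never end follow-up, so the table of TEAEs leading to discontinuation presupposes 4.6.* A subject may withdraw consent because of an AE, which 5.2.4 permits. The table is merely undefined as to treatment or study discontinuation.
- *Long or unresolved reactions will be under-reported in general.* This does not hold for reactions recorded as AEs, and no document indicates how many safety withdrawals to expect.

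**Conclusion.** The contradiction between 4.6 and 6.3 on one side and 5.2.4 on the other is in the text, and the documents do not settle whether subjects withdrawn by the investigator still supply the scheduled data. Separately, SAP 7.4.1 treats a CTR present at the last diary entry as finished, whatever ended the diary. This can lower its duration by one to three classes.

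The reach is limited to the diary duration of CTRs not raised to AEs, detection of new later AEs, and observed Week 6 ratings. Each misclassed subject moves a percentage by 1.9 points if 52 are treated, or 2.1 if 47 are. The total cannot be estimated, because it depends on an unstated number of early exits and on how many of those subjects have a CTR that would have continued. The Day 1 pain comparison is essentially unaffected, and the sample size does not change. A reader might infer that the safety profile is unreliable; the documents do not support that, given the separate AE follow-up. The point is worth correcting because CTR duration is a stated safety endpoint and the remedy costs little.

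**What to change.** **Protocol.** Reconcile 4.6, 6.3 and 5.2.4 so that they state one rule on whether a subject withdrawn by the investigator continues the data collection already scheduled (diary, AE review, Week 6 rating). This concerns data collection only. Which clinical or treatment-stopping rule applies is for the sponsor and investigators to settle.

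**SAP 7.2 and 7.4.1.** Report any CTR present on the last diary day as ongoing, that is, censored with the recorded length as a minimum duration, and show these separately in the duration table. List the day of and reason for withdrawal for the subjects concerned. State whether a TEAE leading to discontinuation means discontinuation of treatment or of the study.

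**Cost.** A few sentences in each document, slightly more analysis work, and a CTR duration table that may look somewhat less favourable. If the reconciled rule keeps such subjects in follow-up, they attend visits that are already scheduled.

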5 STUDY PROCEDURES

5.1 Schedule of events by visit

The Schedule of Events is presented in [Appendix 11.1](#).

Visit 1 – Screening/Enrollment (Day 1/Baseline)

The following procedures will be performed at Visit 1:

Pre-treatment assessments:

- Obtain written informed consent. A subject must be informed of the study requirements, including the risks and benefits of participation. An IEC/IRB-approved informed consent must be signed and dated by the subject prior to any study-related activities or procedures being performed, including discontinuation of any prohibited medications.
- Record demographics/medical history.
- Review and record concomitant medications/procedures.
- Perform urine pregnancy test (if female of childbearing potential). Negative test required prior to randomization.
- Have blinded evaluator (i.e., a qualified healthcare practitioner delegated by the treating investigator and trained by the sponsor) independently perform the Merz Nasolabial Fold (NLF) Scale assessment.
 - **NOTE:** Every effort should be made to ensure that the same blinded evaluator perform the NLF scale assessment at each visit.
- Take standardized NLF baseline photographs.
- Treating physician confirms that the subject meets all eligibility criteria prior to randomization.
- Recall that no anesthesia or other methods to minimize pain (e.g., Tylenol®, ice or ice compress, topical anesthetic, local nerve block) are allowed before NLF injection. *That is, no pre-treatment forms of facial pain reduction are allowed on Day 1.*
- Randomize subject to Belotero Balance injections (Test or Control product by NLF, Subject's right or left NLF injected first). All subject randomization codes will be generated by an electronic system.
- [REDACTED]

Injection and accompanying assessments:

- Administer treatment injections, **not to exceed the maximum allowable injection volume of 3 mL per NLF over the two treatment sessions (initial injection on Day 1 and optional touch-up injection at Week 2).**
 - Document volume injected into each fold (right and left) in the eCRF.
 - Document injection technique (i.e., serial puncture and/or linear threading) in the eCRF.
 - **NOTE:** The same injection technique must be used for both NLFs on Day 1.
- Administer VAS pain assessment for each NLF at time zero (i.e., the time the last injection needle is removed from each NLF, separately, after a full correction).
- Administer Subject Pain-Preference Assessment (three questions) after treatment of both NLFs (i.e., immediately after the time-zero pain VAS assessment).

Additional visit 1 assessments:

- Record any AEs.
- Dispense subject diary and discuss completion instructions.
- Schedule 72-hour follow-up phone call.
- Schedule Visit 2.

Follow-up phone call (72-hours post treatment): Day 4 (\pm 1 day)

- Review and record changes in concomitant medications/procedures.
- Review and record any AEs reported by the subject.
- If subject reports a safety concern, arrange an unscheduled visit to address.
- Remind subject to record CTRs in the subject diary.
- Schedule and/or confirm Visit 2.

Visit 2 (Week 2): Day 14 (+ 3 days)

- Review and record any changes in concomitant medications/procedures.
- Review and record any adverse events.
- Review and collect subject diary. Record subject-reported CTRs in the eCRF. The investigator will review and initial the diary and determine if any entries should also be recorded as AEs on the AE eCRF.

For subjects receiving a touch-up injection at Week 2:

All subjects without ongoing, treatment-related, investigator-reported AEs are eligible for an optional touch-up treatment, at the investigator's discretion and to achieve optimal correction, at Week 2.

- Perform urine pregnancy test (if female of childbearing potential).
- Administer touch-up injection, **not to exceed the maximum allowable injection volume of 3 mL per NLF over the two treatment sessions (initial injection on Day 1 and optional touch-up injection at Week 2)**.
- Dispense subject diary and discuss completion instructions.

Visit 3 (Week 6): Day 42 (+ 3 days)

- Review and record any changes in concomitant medications/procedures.
- Review and record any adverse events.
- Perform urine pregnancy test (if female of childbearing potential).
- Take standardized NLF photographs.
- Have blinded evaluator independently perform the Merz Nasolabial Fold (NLF) Scale assessment.
 - **NOTE:** Every effort should be made to ensure that the same blinded evaluator perform the NLF scale assessment at both visits.
- [REDACTED]
- [REDACTED]
- [REDACTED]
- [REDACTED]
- [REDACTED]
- [REDACTED]
- Review and collect subject diary. Record subject-reported CTRs in the eCRF. The investigator will review and initial the diary and determine if any entries should also be recorded as AEs on the AE eCRF.

5.1.1 *Scheduled visits*

All scheduled visits and applicable study assessments must occur as noted in [Section 5.1](#) and the Schedule of Events table ([Appendix 11.1](#)).

5.1.2 *Unscheduled visits*

To ensure subject safety during the study, any subject who requires additional follow-up during the study for any reason (that does not fall on a scheduled study visit) should have that visit recorded as an unscheduled visit; additionally, all applicable eCRFs for that unscheduled visit should be completed (e.g., AEs, concomitant medications/ procedures).

5.2 *Stopping rules*

5.2.1 *Criteria for treatment discontinuation*

If study treatment is discontinued at any time during the treatment administration, the investigator will record the reason for treatment discontinuation in the study records. The investigator may request that a subject discontinuing treatment continue to participate in the study and complete all remaining visits and assessments. If a subject declines to continue study participation, the investigator will make every effort to perform the appropriate assessments specified in the Schedule of Events ([Section 5.1](#) and [Appendix 11.1](#)).

5.2.2 *Premature suspension or termination of the study*

Should the investigator, sponsor, the FDA, or local regulatory authorities become aware of conditions arising during the conduct of this study that may warrant the cessation of the study, such action may be taken. Prior to such action, consultation between the sponsor, the investigator, and, as appropriate, the FDA and/or local regulatory authorities will occur.

In the case of a reported vascular embolic event leading to skin necrosis, vision loss, or stroke, the study will be suspended, and a root-cause investigation will be conducted to determine the cause of the embolic event and whether the outcome was anticipated or unanticipated. If the latter situation is observed, the entire study will be immediately suspended and no subjects will be enrolled until the event can be properly characterized and an appropriate treatment strategy to avoid this unanticipated event can be devised.

Reasons for the premature suspension or termination of the study include, but are not limited to, the following:

- Determination of a potential safety risk to subjects;
- Inadequate subject enrollment;
- Decision by the IEC/IRB to suspend or terminate approval/favorable opinion for the study;
- Sponsor decision; and/or

- Other.

In the event of premature study suspension or termination for safety reasons, the sponsor will inform all investigators and relevant regulatory authorities promptly of the study suspension/termination and reason for the action. The investigator will conduct site-closure activities in accordance with all applicable sponsor and local/international guidelines and regulations.

5.2.3 *Study site discontinuation*

Study participation by individual sites may be discontinued by the sponsor for any of the reasons listed in [Section 5.2.2](#). Additional reasons for the premature discontinuation of study sites include, but are not limited to, the following:

- Investigator request;
- Serious or persistent noncompliance with the protocol, local regulations, and/or GCP;
- Failure to accrue subjects at an acceptable rate;
- Ethical issues; and/or
- Other.

In the event of study site discontinuation, the sponsor will provide to the study site written notification documenting the reason for discontinuation. The investigator will conduct site-closure activities in accordance with all applicable sponsor and local/international guidelines and regulations.

5.2.4 *Discontinuation criteria for a subject*

Each subject will be followed to the end of the study, or if/when the sponsor decides to terminate the study, whichever comes first. The only reasons a subject will not be followed for all scheduled visits are withdrawal of consent or lost to follow-up (e.g., moving away from study site; unresponsive to attempts to contact the subject).

If a subject withdraws consent to continue in the study, the investigator should make every attempt to complete the final study visit. If a non-serious AE is unresolved at the time of the subject's final study visit, an effort will be made to follow-up until the AE is resolved or stabilized, the subject is lost to follow-up, or there is some other resolution of the event. The investigator should make every attempt to follow all SAEs/UADEs to resolution. Information on pregnancy and the outcome for any female who becomes pregnant during the study will be collected. Additional information on subject withdrawal criteria is provided in [Section 4.6](#).

5.2.5 *Provision of care for subjects after study discontinuation*

The investigator is responsible for ensuring the adequate and safe medical care of subjects during the study. After completion of the study, the sponsor will follow all applicable local or international regulations and guidelines with regard to follow-up care for subjects. The investigator will ensure that appropriate consideration is given to a subject's post-study care.

